### 3 Study design

This study uses a single-cohort, 2-treatment arm, randomized (1:1 (70 mg: placebo)), double-blind study design in adult subjects with chronic migraine (see [Figure 3-1](#)), followed by an open-label treatment period.

Subjects with co-existing Medication Overuse (MO) of triptans, ergot-derivatives, analgesics and combination drug use will be allowed in the trial.

MO will be considered present if any of the following criteria are met during baseline period.

- $\geq 15$  days of simple analgesics
- $\geq 10$  days of triptans
- $\geq 10$  days of ergots
- $\geq 10$  days of combination therapy intake of any combination of ergots, triptans, combination-analgesic medications or simple analgesics

The following periods are included in the study design, with study visits at 4-week intervals after completion of screening:

- **Screening (up to 2 weeks):** to assess initial eligibility

- **Baseline (4 weeks)** diary compliance and headache frequency will be assessed for a final eligibility assessment prior to randomization and dosing. The maximum duration for the baseline period is 35 days. During the COVID-19 pandemic that limits or prevents on-site study visits, the duration of the baseline visit can be extended up to 50 days.
- Eligible subjects will be randomized 1:1 to once monthly erenumab 70 mg and placebo within each of the 4 strata below:
  - prior prophylactic migraine treatment failure and MO
  - prior prophylactic migraine treatment failure and non-MO
  - non-prior prophylactic migraine treatment failure and MO
  - non-prior prophylactic migraine treatment failure and non-MO
- **Double-blind treatment (12 weeks):** Eligible subjects will be randomized to one of two treatment arms. At the end of this period (Week 12), the final assessment to address the efficacy-related objectives will occur.
- **Post double-blind treatment follow-up (12 weeks):** for subjects discontinuing treatment during the double-blind treatment period and willing to return for the subsequent scheduled follow-up (FUP) visits, until the Week 12 follow-up visit.

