 To be completed during applicable study visits before study drug administration.

 Adverse Events will be collected after Informed Consent signature through the end of the Follow-Up Period (12 weeks after the last dose of study drug)  
[REDACTED].

 Study drug is administered by study staff, every 4 weeks ( $\pm$  5 days) during the applicable study visits. One pre-filled syringe will be administered at each visit.

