- 6. its outcome (i.e. recovery status or whether it was fatal)

Conditions that were already present at the time of informed consent should be recorded in medical history of the subject.

Adverse events (including lab abnormalities that constitute AEs) should be described using a diagnosis whenever possible, rather than individual underlying signs and symptoms.

Once an adverse event is detected, it must be followed until its resolution or until it is judged to be permanent (e.g. continuing at the end of the study), and assessment must be made at each visit (or more frequently, if necessary) of any changes in severity, the suspected relationship to the interventions required to treat it, and the outcome.

Information about adverse drug reactions for the investigational drug can be found in the Investigator's Brochure (IB).

Abnormal laboratory values or test results constitute adverse events only if they fulfill at least one of the following criteria:

- they induce clinical signs or symptoms
- they are considered clinically significant
- they require therapy

Clinically significant abnormal laboratory values or test results must be identified through a review of values outside of normal ranges/clinically notable ranges, significant changes from baseline or the previous visit, or values which are considered to be non-typical in subjects with the underlying disease. Alert ranges for laboratory and other test abnormalities are included in [Section 16.1](#)

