### **Adverse events**

The Medical Dictionary for Regulatory Activities will be used to code all adverse events (AEs). A treatment-emergent adverse events (TEAE) is defined as any adverse event that develops after initiation of study treatment until the end of the last study visit or any event already present that worsens following exposure to the study treatment until the end of the last study visit. Subject incidence rates of TEAEs will be tabulated by SOC and PT by treatment group, separately for the double-blind period [REDACTED]. Tables of TEAE by maximum toxicity grade, fatal AEs, serious AEs, AEs leading to withdrawal from investigational drug, treatment-related AEs, and serious treatment-related AEs will also be presented in a similar format as TEAE. Additionally, a listing of subject with TEAE will be presented. The TEAEs identified as potential risk will be summarized separately.

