2.1.4.2 Safety endpoints

Subject Incidence

The subject incidence for a given event in a given period is defined as the number of subjects with at least one reported occurrence of the event divided by the number of subjects who entered that period. For subjects with multiple occurrences of the same event, the event will only be counted once per subject.

Exposure-Adjusted Subject Incidence Rate

The exposure-adjusted subject incidence rate for a given event in a given period is defined as the number of subjects with at least one reported occurrence of the event in a given time period divided by total subject years at risk in that period. The time at risk for each subject will differ for each adverse event. For subjects with events, only the time until the first event contributes to the total subject years at risk. For subjects who do not experience the event, the time at risk will be up to the last available visit. This rate will be presented per 100 subject years. For subjects with multiple occurrences of the same event, the event will be only counted once per subject.

Treatment-Emergent Adverse Event (TEAE)

Adverse Events (AEs) recorded on the Adverse Events eCRF page that occurs on or after first dose of investigational product and up to and including end of study.

Serious Adverse Event (SAE)

SAEs determined by the flag indicating if the adverse event is serious on the Adverse Events eCRF page will include those that occur after signing of the informed consent and up to and including end of study.

Treatment-Emergent Serious Adverse Event

A treatment-emergent serious adverse event is an SAE considered to be treatment-emergent.

Treatment-Related Adverse Event

A treatment-related AE is defined as a treatment-emergent adverse event that is considered by investigators to have reasonable possibility that it may have been caused by IP as determined by the flag indicating that there is a reasonable possibility that the AE is related to investigational product on the Adverse Events eCRF page.

Treatment-Related Serious Adverse Event

A treatment-related serious adverse event is an SAE considered to be treatment-related.

Adverse Event leading to discontinuation of study treatment

An AE leading to discontinuation of study treatment will be identified by the item “Action Taken With Study Treatment” on AE page of CRF when it’s reported as “Drug withdrawn”.

Serious Adverse Event leading to discontinuation of study treatment

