 - Change from baseline in migraine-related disability and productivity as measured by modified MIDAS during the last 4 weeks of the 12-week treatment period (as defined in [Section 2.6](#))
 - Adverse events (as defined in [Section 2.7.1](#))

3 Sample size calculation

The planned total sample size in this proposed China-centric phase 3 study is 550 subjects. The key assumptions in calculating the sample size are based on prior results from erenumab global pivotal study. A treatment difference in terms of change from baseline on MMDs during Week 9-12 (primary endpoint) for erenumab 70 mg vs. placebo is assumed at -2.0 days. The common standard deviation of the primary variable is assumed at 6.8. Given a 1:1 randomization ratio among erenumab 70 mg and placebo, it requires a total of 550 subjects (including 10% drop out rate) to achieve approximate 90% power to demonstrate the treatment difference of erenumab 70 mg compared with placebo under two-sided 0.05 alpha level. The impact of spending alpha at unblinded interim analysis on sample size and power is relatively negligible. Having this interim analysis with alpha spending at 0.014 two-sided, at final analysis an observed p-value ≤ 0.046 two-sided would be required (given that the interim analysis was performed when 70% subject finished treatment or early withdraw). With that said, the overall power will be maintained at approximately 88% with planned sample size.

The sample size for Chinese sub-population will make sure the consistency of treatment effect between Chinese and total population. The methods for consistency assessment are proposed as,

$\Pr(D_{\text{China}} / D_{\text{overall}} > 0.5) > 95\%$,

which means that this China study should have high probability ($>95\%$) to demonstrate consistency where the treatment effect (treatment difference of erenumab compared with placebo) observed in the Chinese population should be as high as at least 50% of the treatment effect observed in the overall study population in the prospective trial, assuming there is no difference between the Chinese population assessed in the trial and the overall population.

To meet the above criteria, approximately 350 (out of 550 for the overall study) Chinese subjects will be recruited.

At the interim analysis, as long as China population takes the majority of the overall population, there should have high likelihood to demonstrate the consistency as well.

4 Change to protocol specified analyses

Not applicable.

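### The SAP's definition of a treatment-emergent adverse event leaves out the protocol's worsening clause without declaring it, so events that start before dosing and worsen on treatment may be missed in the TEAE and treatment-related tables

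*SAP*

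**What the plan says.** Protocol 12.5.2 (Adverse events) gives a TEAE two parts. The first is new onset: "any adverse event that develops after initiation of study treatment until the end of the last study visit". The second is worsening: "any event already present that worsens following exposure to the study treatment until the end of the last study visit".

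SAP 2.1.4.2 has one part only: an AE recorded on the AE page "that occurs on or after first dose of investigational product and up to and including end of study". SAP Section 4, headed "Change to protocol specified analyses", is marked as not applicable.

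AE recording begins well before dosing. Protocol Table 8-1, footnote 14, states: "Adverse Events will be collected after Informed Consent signature through the end of the Follow-Up Period". For an AE once detected, Protocol 10.1.1 requires follow-up until it resolves or is judged permanent, and adds that "assessment must be made at each visit (or more frequently, if necessary) of any changes in severity".

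**The concern.** The two documents define the same term differently, and the SAP, which will be programmed, has the narrower version. Take a subject with grade 1 constipation that starts in the baseline period and reaches grade 2 after the first injection. The protocol counts a TEAE. Read literally, the SAP does not, because the event began before the first dose.

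The definition matters because SAP Table 2-4 builds its principal AE summaries on it, and safety and tolerability is a stated secondary objective. Protocol 1.1 already lists constipation, muscle spasm and pruritus as identified adverse drug reactions. Any of these could be present before dosing and worsen on drug, and that is the case the protocol's second clause covers. Because Section 4 declares no change, a reader of the study report would assume the protocol's definition had been applied.

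**Working it through.** There is no stated figure to reproduce. The check compares the two texts and then traces where the definition is used.

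1. **New onset.** Protocol 12.5.2 and SAP 2.1.4.2 agree in substance: onset from the start of treatment to the end of the study.

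2. **Worsening of an event already present.** Protocol 12.5.2 includes it. SAP 2.1.4.2 has no counterpart.

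3. **Does other SAP text restore it?**
   - SAP 5.1.2 imputes missing or partial start dates only.
   - SAP 5.2 describes the CTCAE grades but gives no rule for a change in grade.
   - SAP 2.7.4.2 mentions worsening for hypertension only, in a separate blood-pressure summary.
   - SAP Section 4 declares nothing.

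   The clause is therefore absent, not moved elsewhere.

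4. **Pre-dose window in which an AE can start** (Protocol Section 3: screening up to 2 weeks; baseline 4 weeks, maximum 35 days, extendable to 50 days in the pandemic):
   - nominal: 14 + 28 = 42 days
   - maximum baseline: 14 + 35 = 49 days
   - COVID-19 rule: 14 + 50 = 64 days

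   Protocol 8.1 also lets the sponsor extend screening in rare cases, which is not included here.

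5. **Tables that depend on the definition** (SAP 2.1.4.2 and Table 2-4):
   - all TEAEs, by SOC and PT, by maximum CTCAE grade, and by PT only, each as incidence and as exposure-adjusted incidence
   - treatment-related AEs, which the SAP defines as a subset of TEAEs
   - treatment-related SAEs, through the meaning of treatment-related

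6. **Outputs that do not depend on it:**
   - SAEs, which are counted from consent
   - AEs leading to discontinuation, which are identified from the action taken with study treatment
   - the listings of all AEs

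7. **Scale.** The documents give no rate of AEs ongoing at Day 1 and no rate of worsening, so the number affected cannot be calculated. With 275 subjects planned per arm (SAP 1.1), one omitted subject changes any single incidence row by at most 1/275 = 0.36 percentage points.

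**The case against.** The strongest reply is that the loss depends on how worsening is recorded, and the documents do not settle this. A reader might infer from Protocol 10.1.1 that a worsened event stays on its first record and keeps its pre-dose start date, so that it is certain to be lost. That section requires follow-up of severity. It does not say whether a higher grade opens a new record or which start date applies. If sites enter worsening as a new AE after dosing, the SAP wording captures it. Two places lean that way: the protocol's SAE definition (10.1.2) includes worsening of pre-existing conditions, and SAP 2.7.4.2 takes worsening hypertension from AE data. This stands as a limit on the consequence. It does not remove the conflict, because no recording rule is written in either document.

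The exposed group is also narrow. Protocol 10.1.1 sends conditions present at consent to medical history, so an AE entered for their on-treatment worsening would have a post-dose start and would count. Only AEs that start between consent and first dose, are still ongoing and then worsen are at risk.

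A reader might also infer that serious worsening disappears. It does not disappear from the overall SAE tables, which have no TEAE condition. The SAP defines a treatment-emergent SAE, but Table 2-4 has no row for it. These outputs are called largely unaffected, rather than wholly, because SAP Table 2-1 starts the double-blind phase after the first dose and does not say how an event with earlier onset is assigned.

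Finally, nothing shows that the omitted events would be mainly high-grade: a change from grade 1 to grade 2 is also worsening. SAP 2.7 plans no between-group testing of safety, so no inferential result depends on this.

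**Conclusion.** The SAP's TEAE definition conflicts with the protocol as written, and the change is undeclared. That part rests on the texts alone and needs no assumption.

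The consequence is conditional. If worsening is kept on a record with a pre-dose start date, AEs that start in the 42 to 64 days before dosing and worsen on treatment would be left out of the TEAE and treatment-related tables. If worsening opens a new record, they would be counted. The number is unknown and probably small, and the affected outputs are descriptive. The point deserves correction because it determines which events enter the main safety tables and costs little to settle. The documents do not support a claim that safety is materially understated.

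**What to change.** - In SAP 2.1.4.2, restore the protocol's second clause, so that a TEAE is an AE with onset on or after first dose, or one already present that worsens after exposure.
- State how worsening is derived. The protocol does not define it, so the SAP has to choose. Two workable options are a post-dose CTCAE grade above the pre-dose grade, or a new AE record with its own start date at worsening. The first needs grade changes to be captured with dates; the second needs a CRF completion instruction.
- Carry the definition through to treatment-related AEs and treatment-related SAEs.
- If the narrower definition is intended, declare and justify it in SAP Section 4.

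The cost is a few lines of SAP text, one derivation flag and possibly a CRF completion note. No extra assessments are needed. If sites already open a new record at worsening, one sentence recording that rule settles the derivation.

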2.1.4.3 Other endpoints at Baseline

Beck Depression Inventory (BDI)-II

The BDI-II is a 21-item questionnaire that assesses severity of depression. Each item is scored from 0 to 3. The total score is calculated by special algorithm and categorized into 4 severity grades: minimal depression (0-13), mild depression (14-19), moderate depression (20-28), and severe depression (29-63). Subjects will complete the BDI-II using the eDiary at screening visit. The recall period is the preceding two weeks, including the day of completion. The BDI-II will only be reported during screening period.

Please refer to [Appendix 5.9](#) for details.

2.2 Analysis sets

The following analysis sets are defined for the double-blind treatment period:

The **Full Analysis Set (FAS)** includes all subjects who were randomized in the study. Subjects will be analyzed according to their randomized treatment, regardless of the treatment received. Tabulations of demographic and baseline characteristics, disposition, important protocol deviations (IPDs), and efficacy analyses will utilize this analysis set.

The **Safety analysis set (SAF)** will consist of all randomized subjects who received at least one dose of investigational product. In SAF, subjects will be analyzed based on actual treatment received. Safety analyses will be performed based on SAF.

The following analysis set is defined for the open-label treatment period:

The **Open-label treatment analysis set (OAS)** will consist of all subjects who consented to enter into the open-label treatment period and who have taken at least one dose of erenumab during the open-label treatment period. This analysis set will be used when summarizing data collected during the open-label treatment period.

2.2.1 Subgroup of interest

The primary and secondary efficacy endpoints, safety endpoints (adverse events, clinical laboratory values, vital signs, and anti-AMG 334 antibodies), as well as the demographics and baseline characteristics, and the prior migraine prophylactic medication usage information will be analyzed for Chinese subgroup (recruited from China mainland and 3 qualified sites from Taiwan). This is to evaluate the consistency of efficacy and safety effects in Chinese population vs overall population.

In addition, the effect in the following subgroup analysis by baseline characteristic will be investigated with respect to the primary and secondary efficacy analyses as well:

- Prior prophylactic migraine medication treatment failure (Yes or No)
- Medication overuse at Baseline: Yes, No

- Baseline MMD (< median vs \geq median)
- Disease duration (< median vs \geq median)
- Age (< median vs \geq median)
- BMI (< median vs \geq median)
- Sex (Male vs Female)
- Region

The impact of other baseline variables, may be investigated with respect to the primary and secondary efficacy analyses if, upon clinical review, differences between treatment groups are deemed clinically meaningful.

The purpose of the subgroup analyses is to explore if the treatment effect varies across subgroups of interest. Subgroup analyses are performed for primary and secondary efficacy endpoints using the same method as primary analysis method but performed within each subgroup of interest. The treatment difference (or odds ratio) with associated 95% confidence intervals and p-values will be reported within each subgroup.

Note: if the subgroup is the stratification factor (Prior prophylactic migraine medication treatment failure) then it will not be included in the model.

The heterogeneity of the treatment effect across the subgroups will be evaluated for the primary and secondary endpoints by examining the treatment by subgroup interaction and the p-value for the interaction term will be reported. For continuous endpoints, the primary analysis model with the addition of subgroup and treatment group by subgroup interaction as two additional effects will be used. For endpoint based on proportions, a logistic regression model that includes treatment group, stratification factors, baseline value, subgroup and treatment group by subgroup interaction will be used.

If the value of the group variable cannot be determined, the subject will be excluded from the corresponding subgroup analysis. For each subgroup analysis, if, in any treatment group, the number of subjects is less than 10 for a subgroup, then only summary statistics will be performed.

The adjusted mean changes from baseline, SE's, and 95% CIs for each subgroup and the nominal p-value for subgroup by treatment interaction will be calculated.

The outcome will be displayed in separate forest plot for each endpoint with the following information:

- The number of patients within each subgroup level / treatment arm
- Supporting information such as least squares mean by treatment and subgroup level
- The treatment effect (erenumab 70mg vs. placebo) estimate and two-sided 95% confidence interval within each subgroup level (using the BY statement for the primary analysis model).
- The directions which favor placebo or AMG 334 will be indicated.
- p-value for the treatment*subgroup interaction term.

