A Phase 2 study, Study 20120309, was conducted in Japan in the EM population. While the results were significant for all three doses evaluated (28 mg, 70 mg and 140 mg), the efficacy on the primary endpoint for the 28 mg dose was almost 50% lesser in magnitude than the 70 mg dose. Therefore, the 28 mg dose is not considered a clinically relevant dose given the similar safety profile between three doses. Comparable efficacy was seen between 70 mg and 140 mg doses in primary endpoint and all secondary endpoints, whereas maximal efficacy was observed with the 140 mg dose in the global Study 20120296. This study showed comparable exposure-response characteristics between the overall global and the Japanese population. The clinically relevant dose of 70 mg is consistent with the overall higher exposure associated with lower body mass index BMI/body weight in Japanese population, which likely led to the lack of incremental efficacy benefits in Study 20120309 between the 140 and 70 mg dose that were observed in the overall global population. This difference does not reflect any meaningful differences in ethnic sensitivity.

Similar BMI/body weight was observed between Chinese and Japanese based on prior study results in the same subject population. Since the body-weight was the only important covariate identified with the population PK modeling, we do not expect that other demographic/ethnic factors might be associated with a relevant difference between global and Japanese and/or Chinese population. Consequently, the 70 mg is likely also the appropriate efficacious dose in Chinese population. Although this study was conducted in the EM population, numerous lines of evidence that support they are a continuum of the same disorder ([Section 1.1](#)).

The combination of Study 20120295 and Study 20120309 are therefore considered most informative for the dose selection and support the selection of the 70 mg dose in this study.

The 12-weeks double-blind study duration is endorsed by IHS guidelines as a sufficient duration to assess efficacy in prophylactic migraine treatment clinical trials. A longer double-blind trial duration is not considered feasible due to the prolonged placebo exposure.

Subjects will receive either erenumab 70 mg q.m. s.c. or matching placebo for 12 weeks in the double-blind treatment period, followed by erenumab 70 mg q.m. s.c. in the open-label treatment period.

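### Effect modification by baseline MMD, disease duration, age and BMI is tested only after a median split, which weakens the test if modification is smooth; body weight is not tested at all

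*SAP*

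**What the plan says.** SAP 2.2.1 lists eight baseline subgroup variables besides the Chinese subgroup. Four are continuous, and each is defined only by a cut at the median: "Baseline MMD (< median vs \geq median", "Disease duration (< median vs \geq median", "Age (< median vs \geq median" and "BMI (< median vs \geq median" (closing brackets omitted).

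The declared aim is exploratory: "The purpose of the subgroup analyses is to explore if the treatment effect varies across subgroups of interest". Heterogeneity is to be evaluated "by examining the treatment by subgroup interaction and the p-value for the interaction term will be reported". For continuous endpoints, the heterogeneity test is the primary model with the "addition of subgroup and treatment group by subgroup interaction as two additional effects will be used". For proportions, it is a logistic model with the same two terms. The interaction p-value is called nominal, and it appears on a forest plot for each endpoint beside the within-level estimates and 95% confidence intervals.

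Protocol 4.2 argues for 70 mg partly from higher exposure at lower BMI or body weight. The covariate that it takes from the PK modelling is weight: "Since the body-weight was the only important covariate identified with the population PK modeling". Weight is measured at screening, baseline and end of treatment (Protocol Table 8-1) and summarised at baseline (SAP 2.3.2), but it is not among the subgroup variables.

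**The concern.** A median split treats a subject just below the cut as different from one just above it, and as identical to one at the minimum. If the treatment effect drifts smoothly with the covariate, the within-half variation carries information that the planned test does not use. Baseline MMD shows the contrast: it already enters the primary model as a baseline covariate, yet its interaction with treatment is tested on two levels.

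What is at stake is how well an exploratory analysis serves its own purpose. The data to do better are already collected. The BMI test has some added interest because BMI is the only listed variable close to the weight argument in Protocol 4.2.

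**Working it through.** **Inputs from the documents.** Difference -2.0 days, SD 6.8, 1:1 allocation, two-sided 0.05, 550 subjects including 10% dropout, power about 90% (Protocol 12.8.1). Evaluable: 550 × 0.90 = 495.

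**Assumed, not in the documents.** The distribution of each covariate and the shape of any effect modification. The base case is a normal covariate with linear modification; other shapes are shown as a range.

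**The plan's own figure first.** n per arm = 2 × (1.960 + 1.282)² × 6.8² / 2.0² = 243, or 486 in total; 486 / 0.90 = 540, close to 550. With 495 evaluable, power is 90.5% at 0.05. With the 0.014 and 0.046 thresholds at 70% information it is 90.2%. The inputs reproduce. The documents state no power for any interaction test.

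**Relative efficiency.** For a linear modifier X, the split test has efficiency corr(X, 1[X ≥ median])² relative to the continuous test. For a normal X this is 2/π = 0.637, a loss of 36.3%. Then 495 subjects act like 495 × 0.637 = 315, and equal power needs 1/0.637 = 1.57 times as many.

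| Assumed covariate shape | Loss |
|---|---|
| Uniform | 25% |
| Age, normal truncated to 18–65 | 28–33% |
| Baseline MMD, normal truncated to 8–28 | 30–33% |
| Normal | 36% |
| Mildly skewed (lognormal, sigma 0.15–0.3) | 38–41% |
| Strongly skewed (exponential; lognormal, sigma 0.6) | 52–53% |

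**Power, single time point, normal covariate, N = 495.**

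- Continuous: SE of the change in effect per SD of covariate = 2 × 6.8 / √495 = 0.611.
- Split: difference between halves = 2 × √(2/π) × slope = 1.596 × slope, with SE = 4 × 6.8 / √495 = 1.223.

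| Slope (days per SD) | Continuous | Split |
|---|---|---|
| 0.5 | 13% | 10% |
| 1.0 | 37% | 26% |
| 1.5 | 69% | 50% |
| 2.0 | 91% | 74% |

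For slope 1.5: continuous z = 1.5 / 0.611 = 2.45; split z = 2.394 / 1.223 = 1.96. Simulation of ordinary least-squares interaction tests gave 68% and 49% at 1.5, and 36% and 24% at 1.0, with both tests near 5% when there is no interaction.

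**The opposite case.** If the effect instead jumps at the median by the same between-half difference (2.39 days, the 1.5 equivalent), simulated power is 51% for the split test and 36% for the continuous one.

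**The case against.** The strongest reply is that a pre-specified median split with forest plots is a workable exploratory choice on which no decision rests. That stands, and it limits the point to a refinement. Several further objections also stand, in whole or part.

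- A reader might take 36% as a fixed property of the plan. It is not: it needs a normal covariate and linear modification. Age and baseline MMD are bounded, disease duration may be skewed, and a step at the median would favour the split.
- A reader might infer that BMI underlies the choice of 70 mg, so that the BMI interaction is the trial's own check on the dose. Protocol 4.2 does not support this. It names body weight as the PK covariate, mentions BMI only together with weight, and rests the dose on Studies 20120295 and 20120309. The weight argument concerns the lack of added benefit of 140 mg over 70 mg, and this trial has only 70 mg and placebo.
- A reader might infer that a null interaction p-value will serve as evidence of consistency. The documents' consistency criterion is the ratio of the Chinese to the overall effect (Protocol 12.8.1, SAP 3), not these p-values.
- The slopes of 1.5 and 2.0 are large against an overall effect of -2.0 days. At 1.5 the effect reaches zero at 2.0 / 1.5 = 1.33 SD and reverses for about 9% of a normal population; at 2.0 it reverses for about 16%. At 0.5 both tests are weak and the gain is about 3 points.
- The powers are for one time point. SAP 2.2.1 adds the terms to the repeated-measures model and states no subgroup-by-visit term, so these are not the powers of the planned test.
- Parts of the SAP are redacted, so absence of a continuous interaction can be confirmed for the visible text only.

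None of this removes the loss under smooth modification. Nothing in the documents suggests a step at the sample median, which is not a clinical threshold.

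**Conclusion.** The point holds as a low-cost improvement. In the visible text, the four continuous modifiers are tested for interaction only after a median split. With a roughly normal covariate and linear modification the loss is about 36% of the information, and about 25% to 53% over the shapes tried. In the single-time-point illustration this is about 19 points of power at 1.5 days per SD and 12 points at 1.0. There is no loss if modification is a step at the median. The primary analysis, its type I error and its conclusion are untouched. Separately, BMI/body weight is part of the case for 70 mg, and the weight variable on which the PK argument turns has no interaction test.

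**What to change.** In SAP 2.2.1, keep the median-split estimates and forest plots as planned. Add one sentence: for baseline MMD, disease duration, age, BMI and baseline body weight, the reported interaction p-value comes from treatment by the continuous covariate in the same model, with the estimated treatment effect and 95% confidence interval at the 25th, 50th and 75th percentiles of the covariate.

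No new data are needed. The cost is five extra models for each of the four endpoints (one primary, three secondary). The downside is a linearity assumption, on the logit scale for the 50% responder endpoint. The retained two-level display checks that assumption only roughly.
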